6. INVESTIGATIONAL PRODUCT

6.1 Name and description of investigational product

This is a non-pharmacological behavioral intervention study. There is no investigational medicinal product or device. The investigational interventions are:

- Structured physical exercise: Chair-based osteoporosis prevention exercise protocol developed by the Indonesian Osteoporosis Association (PEROSI).
- Social heterochronic parabiosis (SHP)-based intergenerational intervention: Direct interactive activities between elderly participants and children using educational materials from the “Ayo Minum Air” (AMIR) program of the Indonesian Hydration Working Group (IHWG), including illustrated comics, simple gymnastics videos, and hydration-focused educational games.

Both interventions are combined sequentially with standard nutritional education (tele-conferences and e-flyers).

6.2 Summary of findings from non-clinical studies

Not applicable. The interventions are non-pharmacological and based on established exercise physiology, geriatrics, and intergenerational program research.

6.3 Summary of findings from clinical studies

Structured chair-based exercise (similar to PEROSI protocol) has been shown in previous studies to improve muscle strength, balance, gait speed, and reduce fall risk in elderly populations, with short (12 weeks) benefits. Sequential multimodal interventions (physical exercise followed by cognitive/social tasks) have demonstrated superior increases in serum BDNF levels compared to the reverse order. Intergenerational programs have shown positive effects on mental health, cognitive function, and social well-being in healthy elderly and youth, with reciprocal benefits. However, no prior studies have specifically evaluated the combination of structured PEROSI exercise followed by SHP-based intervention using AMIR materials in the elderly with PCDS.

6.4 Summary of known and potential risks and benefits

Known risks: Minimal.

- Physical exercise: Mild fatigue, muscle soreness, low risk of fall or strain (mitigated by progressive intensity, supervision, pre-session checks, and termination criteria using Borg scale and ACSM guidelines).
- Blood sampling: Minor bruising, pain, or dizziness at the venipuncture site.
- Intergenerational activities: Initial psychological discomfort (awkwardness or anxiety) in interacting with unfamiliar children or the elderly.
- Overall: Low risk profile comparable to routine community exercise programs for the elderly.

Potential benefits:

- Improved physical function (grip strength, gait speed), reduced frailty, enhanced cognitive performance (MoCA-Ina), increased serum mBDNF (marker of neuroplasticity and muscle-brain axis), and better health-related quality of life.
- Additional benefits: Reduced social isolation, enhanced intergenerational empathy, free nutritional counseling, and health monitoring for participants.

The benefit-risk ratio is considered highly favorable, as the interventions are non-invasive, reversible, and target a reversible condition (PCDS) with established components of low risk.

6.5 Description and justification of route of administration and dosage

Not applicable (non-medicinal product). Justification for “dosage” (intensity/duration):

- Exercise: 12 weeks progressive frequency (1–3 sessions/week, 60 min) based on evidence for sufficient stimulus to improve strength, balance, and neuroplasticity in frail/pre-frail elderly without overload.
- SHP: 4 weeks, 8 sessions (2/week, 45 min) selected to allow meaningful intergenerational bonding and cognitive-social stimulation while minimizing burden on participants and orphanages.

6.6 Preparation and labelling of Investigational Product

Not applicable.

6.7. Preparation of transporting and delivery of investigational product to Indonesia

Not applicable.

6.8 Drug accountability

Not applicable. Exercise sessions and intergenerational activities are documented for adherence (attendance logs, session completion records). Educational materials (e-flyers, AMIR comics/videos) are tracked for delivery/receipt.

7. METHODS

7.1 Study parameters/endpoints

7.1.1 Main study parameter/endpoint

- Change in frailty syndrome status (assessed using Cardiovascular Health Study criteria: score 0 robust, 1–2 pre-frail, ≥3 frail) from baseline to week 16.
- Change in serum mature brain-derived neurotrophic factor (mBDNF) levels (measured by ELISA) from baseline to week 16.

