2. OBJECTIVES

Primary Objectives

To evaluate the effects of 12 weeks of structured physical exercise (chair-based PEROSI protocol) followed by 4 weeks of social heterochronic parabiosis (SHP)-based intergenerational

intervention on frailty syndrome and serum mature brain-derived neurotrophic factor (mBDNF) levels in community-dwelling elderly with physio-cognitive decline syndrome (PCDS).

Secondary objectives

- To analyze the effects of the combined intervention over 16 weeks on hand grip strength in elderly with PCDS.
- To analyze the effects of the combined intervention over 16 weeks on gait speed in elderly with PCDS.
- To analyze the effects of the combined intervention over 16 weeks on cognitive function as measured by the MoCA-Ina score in the elderly with PCDS.
- To evaluate the effects of the combined intervention over 16 weeks on health-related quality of life in the elderly with PCDS.
- To assess correlations between changes in serum mBDNF levels and changes in MoCA-Ina score, hand grip strength, and gait speed in the elderly with PCDS.

Hypothesis

Elderly people with physio-cognitive decline syndrome (PCDS) who receive 12 weeks of structured physical exercise followed by 4 weeks of social heterochronic parabiosis (SHP)-based intergenerational intervention on top of nutritional education have significantly better frailty syndrome status and higher serum mature brain-derived neurotrophic factor (mBDNF) levels than those receiving nutritional education alone after 16 weeks of intervention, along with greater improvements in hand grip strength, gait speed, cognitive function (MoCA-Ina score), and health-related quality of life.

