4.2 Inclusion criteria

For elderly participants:

- Aged 60–75 years
- Meet diagnostic criteria for physio-cognitive decline syndrome (PCDS): gait speed <1.0 m/s and/or hand grip strength <28 kg (men) or <18 kg (women), and MoCA-Ina score 22–26
- Instrumental Activities of Daily Living (IADL) score >5

- Able to understand and follow instructions adequately
- Willing to participate and provide written informed consent

For child participants (intervention group only):

- Aged 5–8 years
- In good health and cooperative
- Able to understand and follow instructions
- Written permission obtained from orphanage management

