4.5 Sample size calculation

The sample size was calculated to detect clinically meaningful differences between the intervention and control groups in key outcome measures, including handgrip strength, gait speed, cognitive function (MoCA-Ina score), health-related quality of life (SF-12), and serum mature brain-derived neurotrophic factor (mBDNF) levels.

Sample size estimation was performed using the formula for comparison of two independent means, with a two-sided significance level (α) of 5% and a statistical power ($1-\beta$) of 80%. The standard deviation and expected mean differences for each outcome were derived from previously published studies involving older adults, as no prior studies have specifically evaluated SHP-based interventions or their combination with structured physical exercise.

Based on these calculations, the required sample sizes for individual outcome parameters ranged from 9 to 42 participants per group. Considering the largest estimated sample size requirement and allowing for potential dropouts, the minimum required sample size for this randomized controlled trial was determined to be 100 older adult participants, with **50 participants allocated to each group (intervention and control)**.

This sample size is considered sufficient to evaluate the primary and secondary outcomes of the study and to ensure adequate statistical power while accounting for potential attrition during the study period.

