7.3.4 Physical and functional performances

- **Hand-grip strength:** Measured using a calibrated hand dynamometer from the American Society of Hand Therapists (ASHT) protocol:
 - Seated position, shoulder adducted/neutral rotation, elbow 90° flexion, forearm neutral, wrist 0–30° dorsiflexion, and 0–15° ulnar deviation.
 - Feet flat on floor, dry hands.
 - Three maximal efforts on the dominant hand with 30-second rest; the highest value recorded (kg).
 - Procedure terminated if pain or discomfort is reported.
- **Gait speed:** 6-meter walk test:
 - 10-meter straight pathway marked at 0, 2, 6, 8, and 10 meters (2m acceleration, 6m timed, 2m deceleration).
 - Usual walking pace, no running, assistive device allowed if habitual.
 - Two trials; time recorded from 2m to 8m mark; average speed (m/s) calculated.
- **Frailty status:** Cardiovascular Health Study (CHS) criteria:
 - Unintentional weight loss (>4.5 kg or >5% in past year).
 - Weakness (grip strength lowest quintile by sex/BMI).
 - Exhaustion (self-reported).
 - Slowness (gait speed lowest quintile by sex/height).
 - Low physical activity (weighted score of kcal/week).
 - Scoring: 0 = robust, 1–2 = pre-frail, ≥3 = frail.
- **Instrumental Activities of Daily Living (IADL):** Lawton scale (score >5 required at inclusion; monitored for changes).

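### The primary frailty endpoint is change in a three-level status, which hides some one-item improvements (mainly 2 to 1) that the 0–5 CHS count, already collected, would show

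*Combined protocol and SAP*

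**What the plan says.** Section 7.1.1 names two main endpoints. The first is "Change in frailty syndrome status (assessed using Cardiovascular Health Study criteria: score 0 robust, 1–2 pre-frail, ≥3 frail", from baseline to week 16; the second is change in serum mBDNF. The hypothesis in section 2 is worded on the same scale: the intervention group is expected to "have significantly better frailty syndrome status and higher serum mature brain-derived neurotrophic factor (mBDNF) levels".

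Section 7.3.4 lists the five CHS criteria (weight loss, weakness, exhaustion, slowness, low physical activity) and repeats the bands: "Scoring: 0 = robust, 1–2 = pre-frail, ≥3 = frail". Section 7.4 has frailty assessed at baseline, at week 12 and, through the repeat of baseline assessments, at week 16. A 0–5 count therefore exists at every assessment, but no section makes change in that count an endpoint or an analysis.

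Two other sections bear on the point. The sample size in section 4.5 rests on outcomes "including handgrip strength, gait speed, cognitive function (MoCA-Ina score), health-related quality of life (SF-12), and serum mature brain-derived neurotrophic factor (mBDNF) levels"; frailty is not among them. Section 9 names the outcomes to be compared between groups, and neither frailty status nor the count is listed.

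**The concern.** Grouping an ordered count into three bands discards every movement inside a band. A participant who is both slow and weak at baseline, with no other positive item, scores 2. If exercise resolves one of these items, the score becomes 1 and the status stays pre-frail, so the participant is recorded as unchanged.

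Over 16 weeks, losing one item is a plausible form of benefit, and section 6.4 expects grip strength and gait speed to improve. The frailty endpoint could therefore read null while the secondary endpoints for grip and gait improve. Adding a frailty test to section 9 would not cure this, because any test of the collapsed status inherits the loss.

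**Working it through.** **The plan's own figure.** The largest requirement in section 4.5 is 42 per group and section 7.6 allows up to 15% drop-out: 42 / 0.85 = 49.4, rounded up to 50, which matches the plan. With 15% lost, 50 × 0.85 = 42.5, so about 43 per arm remain. The range of 9 to 42 itself cannot be recomputed, because no SD or mean difference is given. No figure of any kind is given for frailty.

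**Which steps are visible.** Applying the bands {0}, {1, 2}, {3, 4, 5} to each one-point improvement:

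- 1 to 0: pre-frail to robust, visible
- 2 to 1: pre-frail to pre-frail, hidden
- 3 to 2: frail to pre-frail, visible
- 4 to 3: frail to frail, hidden
- 5 to 4: frail to frail, hidden

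**How many participants this touches** depends on where they start. If each participant with a positive item were to improve by one point, the hidden share would be (scores 2, 4, 5) / (scores 1 to 5). For an assumed baseline of 10/35/35/15/4/1% at scores 0 to 5, that is (35 + 4 + 1) / 90 = 44%, of which 35 / 90 = 39% is the step 2 to 1. For 10/60/20/8/2/0% it is (20 + 2 + 0) / 90 = 24%.

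**Power, by simulation on assumed inputs.** Assumptions: 43 per arm; each positive item resolves with probability 0.15 in control and 0.35 or 0.45 in intervention; each negative item becomes positive with probability 0.05; two-sided 5% Mann-Whitney test on the change; 4,000 replicates for A–C and 2,500 for D–F. None of the resolution rates or baseline mixes comes from the documents.

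| Assumed baseline, scores 0–5 (%) | Count vs status, 0.35 | Loss (points) | Count vs status, 0.45 | Loss (points) |
|---|---|---|---|---|
| A: 10/35/35/15/4/1 | 0.548 vs 0.398 | 15 | 0.833 vs 0.692 | 14 |
| B: 20/35/30/10/4/1 | 0.427 vs 0.290 | 14 | 0.714 vs 0.581 | 13 |
| C: 5/25/40/20/8/2 | 0.667 vs 0.467 | 20 | 0.922 vs 0.780 | 14 |
| D: 10/60/20/8/2/0 | 0.40 vs 0.36 | 4 | 0.73 vs 0.67 | 6 |
| E: 15/65/15/5/0/0 | 0.35 vs 0.34 | 1 | 0.62 vs 0.59 | 3 |
| F: 5/75/15/5/0/0 | 0.42 vs 0.43 | −1 | 0.69 vs 0.71 | −2 |

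Repeat runs of A–C gave losses of 10 to 20 points. The small negative values in F are of the order of simulation error. In A–C, 34–42% of intervention participants whose count improved showed no improvement in status. Type I error in A–C was 4.5–5.1% for both scales.

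**A second model.** Here 42 per arm change by at most one point, 10% worsen, and 40% vs 15% or 50% vs 20% improve. The count had more power in all five baseline mixes tried. The gap ran from 0.522 − 0.505 = 0.017 (heavy at score 1) to 0.651 − 0.256 = 0.395 (heavy at score 2). The direction agrees, and the size again depends on the baseline mix.

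**The case against.** The strongest reply is that nothing here is an error. Robust / pre-frail / frail is the CHS classification as the protocol defines it, and endpoint, measurement and hypothesis all use it. A recognised clinical state is a defensible primary endpoint. That stands: the point concerns efficiency, not inconsistency.

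Four stronger readings are tempting, and the documents do not support them.

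- *Three of five steps are hidden, so 60% of the benefit is lost.* Three of five counts possible steps, not participants. Two of the three need a baseline score of 4 or 5, to which baselines A–C give only 5%, 5% and 10%. In practice the issue is mainly 2 to 1.
- *The trial loses 13–20 points of power.* That range describes baselines A–C only. Entry needs just one physical deficit, and section 4.3 excludes disability, depression and total immobility, so a sample concentrated at score 1 is plausible. The loss is then small or nil.
- *Eligibility places most participants at scores 1–2.* Section 4.2 uses fixed cut-offs: "gait speed <1.0 m/s and/or hand grip strength <28 kg (men) or <18 kg (women), and MoCA-Ina score 22–26". The CHS weakness and slowness items use lowest quintiles by sex and BMI, and by sex and height. A participant can meet the entry cut-offs and be negative on both CHS items.
- *The benefit would be lost to the trial.* Grip strength and gait speed are continuous secondary endpoints in section 7.1.2 and would still show it.

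Two further limits stand. The simulation lets every item resolve at the same rate, yet weight loss is judged over the past year and a 16-week programme cannot readily change it. The power comparison is also between two analyses that section 9 does not specify; that absence is a separate gap.

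**Conclusion.** The concern holds as a loss of sensitivity of uncertain size. It is certain that the status endpoint discards the steps 2 to 1, 4 to 3 and 5 to 4, and that the plan analyses the count nowhere. How much this costs cannot be taken from the documents. Under the item-resolution assumptions, the loss is about 0–6 points of power if most participants start at score 1, and about 10–20 points if scores 1 and 2 are similarly common or score 2 dominates. In no scenario tried was the count materially worse. With no sample size for frailty in section 4.5, the plan shows no margin to absorb such a loss. The change is worth making as an inexpensive improvement; it does not correct a contradiction.

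**What to change.** In section 7.1.1, define the frailty endpoint as change in the CHS count (number of positive criteria, 0–5) from baseline to week 16, analysed as an ordinal score. Keep the robust / pre-frail / frail shift table by arm as the supportive clinical presentation. Reword the frailty part of the hypothesis in section 2 to match. Add the between-group frailty comparison to section 9, naming the test; a Mann-Whitney test on the change, already in that section for other outcomes, would serve.

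No new data are needed. There are two costs. A change in count is less familiar to clinicians than a shift in status, which is why the shift table should stay. Changing a main endpoint also needs a protocol amendment with ethics review under section 11.3. It should be done before any outcome data are seen, since a later change of scale would look data-driven.

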7.1.2 Secondary study parameters/endpoints

- Change in hand grip strength (in kilogram; dominant hand, best of 3 trials using hand dynamometer) from baseline to week 16.
- Change in gait speed (m/s; average of 2 trials over 6-meter walk test) from baseline to week 16.
- Change in cognitive function (MoCA-Ina total score, range 0–30) from baseline to week 16.
- Change in health-related quality of life (SF-12 questionnaire) from baseline to week 16.
- Correlations between changes in serum mBDNF levels and changes in MoCA-Ina score, hand grip strength, and gait speed.

7.1.3. Other parameters (exploratory)

- Adherence to exercise sessions and intergenerational activities (attendance logs).
- Nutritional status (Mini Nutritional Assessment, MNA).
- Physical activity level (Physical Activity Scale for the Elderly, PASE).
- Depressive symptoms (Geriatric Depression Scale-15, GDS-15).
- Loneliness (De Jong Gierveld Loneliness Scale, Indonesian version).
- Quality of life additional domains (EQ-5D-5L).
- Charlson Comorbidity Index (CCI).
- Adverse events and dropout reasons.

7.2 Randomization, blinding, and treatment allocation

Randomization is performed after screening and baseline assessments using computer-generated permuted block randomization (block size 4). Allocation is managed by an independent third party (staff from the Department of Internal Medicine, School of Medicine and

Health Sciences at Atma Jaya Catholic University of Indonesia), not involved in the study. Sequence is concealed until assignment. Participants are allocated 1:1 to intervention or control arm.

Due to the behavioral nature of the intervention, blinding of participants, instructors, and research team is not possible (open-label design). However, laboratory analysts for mBDNF measurement are blinded to group allocation. Outcome assessors for physical measurements (grip strength, gait speed) are trained for consistency (inter-rater reliability tested with Kappa statistic).

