3. STUDY DESIGN

This is a single-center, randomized, open-label (unblinded), parallel-group controlled clinical trial evaluating the efficacy of a sequential multimodal intervention (structured physical exercise followed by SHP-based intergenerational activities) compared to nutritional education alone in community-dwelling elderly aged 60–75 years with physio-cognitive decline syndrome (PCDS).

The study duration per participant is 16 weeks, consisting of:

- Baseline assessment (week 0)
- Intervention period: 12 weeks of chair-exercise + 4 weeks of intergenerational activities (intervention arm) or continued education (control arm)
- Intermediate assessment (end of week 12)
- Final assessment (end of week 16)

Participants are randomized in a 1:1 ratio into two arms:

- Intervention arm (n=50): Nutritional education + 12 weeks structured chair-based exercise (PEROSI protocol, progressive frequency from 1 to 3 sessions/week, 60 minutes/session, supervised online) followed sequentially by 4 weeks SHP-based intergenerational activities (8 sessions, 2x/week, 45 minutes/session, paired 1:1 elderly-child using AMIR educational materials at selected orphanages).
- Control arm (n=50): Nutritional education only (2 personalized dietitian tele-conferences at weeks 1 and 11; 5 educational e-flyers at weeks 3, 5, 7, 13, and 15).

Randomization is computer-generated using permuted block randomization (block size 4), stratified if necessary, with allocation concealment managed by an independent third party. Blinding of participants and instructors is not feasible due to the nature of the behavioral interventions; however, outcome assessors for laboratory analyses (mBDNF) are blinded to group allocation where possible.

The trial follows intention-to-treat principles with per-protocol sensitivity analysis. Recruitment targets consecutive eligible elderly from community programs under the School of Medicine and Health Sciences at Atma Jaya Catholic University of Indonesia and the Archdiocese of Jakarta. Child participants (aged 5–8 years, n=50) are recruited from cooperating orphanages exclusively for the intervention arm.

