5. TREATMENT OF SUBJECTS

Subjects will be randomly assigned to one of two groups: structured physical exercise followed by a social heterochronic parabiosis (SHP)-based intervention (intervention group) or usual care only (control group). Randomization will be computer-generated using a block-permuted randomization method with variable block sizes of four. The randomization list will be held by an independent third party (staff of the Department of Internal Medicine, School of Medicine and Health Sciences, Atma Jaya Catholic University of Indonesia) who is not involved in the research team. Both the investigators and the participants will be blinded to group allocation.

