7.3 Study procedures

All procedures are performed by trained research personnel (principal investigator, assistants, certified instructors). Inter-rater reliability for grip strength and gait speed measurements is established prior to study start (Kappa evaluation on 50 elderly people between the principal investigator and assistants). Assessments are conducted at three time points: baseline (week 0), intermediate (end of week 12, post-exercise phase), and final (end of week 16, post-full intervention). Additional monitoring occurs as described.

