10.1 Recruitment and informed consent

Eligible elderly participants will be informed about the study purpose, procedures, potential risks, benefits, voluntary nature, and right to withdraw at any time without consequence through verbal explanation and written information sheets. Informed consent will be obtained in writing by the principal investigator or trained research assistant, with opportunity for questions. If needed, family members or caregivers may accompany the participant during consent, but the decision remains with the participant.

For child participants (intervention arm only), written permission will be obtained from the orphanage management (as legal guardian representative). Child-friendly verbal explanations will be provided to children, and assent will be sought based on their understanding and willingness. Children may refuse or withdraw at any time.

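### A single printed block size of 4, in an open-label single-centre trial, lets an unblinded recruiting team infer up to a third of allocations in advance if earlier ones are known; varying, undisclosed sizes would largely remove this

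*Combined protocol and SAP*

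**What the plan says.** **Block size.** Section 3 states: "Randomization is computer-generated using permuted block randomization (block size 4), stratified if necessary, with allocation concealment managed by an independent third party". No stratification factor is named anywhere. Section 7.2 repeats the size ("computer-generated permuted block randomization (block size 4") and the ratio ("Participants are allocated 1:1 to intervention or control arm"). Section 5 describes a "block-permuted randomization method with variable block sizes of four". That wording contradicts itself, and no second size appears in the document.

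**Who knows what.** Section 3 describes a single-centre, open-label trial. Section 7.2 says that "blinding of participants, instructors, and research team is not possible (open-label design". Section 5 says instead that investigators and participants are blinded. Only the mBDNF laboratory analysts are described as blinded in a way that fits the design.

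**Who enrols and measures.** Section 10.1: "Informed consent will be obtained in writing by the principal investigator or trained research assistant". Section 7.3: "All procedures are performed by trained research personnel (principal investigator, assistants, certified instructors". One team therefore recruits, assesses eligibility and records baseline.

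**Safeguards already planned.** Section 7.2 places the list with an independent third party, conceals the sequence until assignment, and randomizes after screening and baseline assessment. Section 7.4 also lists randomization after eligibility is confirmed. Section 4.4 has candidates identified consecutively.

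**The concern.** Keeping the list with a third party hides the list. It does not hide what follows from allocations already made. In 1:1 blocks of four, every block holds two of each arm, so anyone who knows the block size and the earlier allocations can work out the end of each block.

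A recruiter who foresees the next arm has three possible levers:
- timing, by bringing a candidate forward or putting one off;
- the entry criteria that call for judgement, such as adequate ability to follow instructions, for which section 4.2 gives no threshold;
- the baseline tests themselves, which the team measures before the allocation is released.

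The third lever matters because the efficacy endpoints in sections 7.1.1 and 7.1.2, apart from the correlations, are changes from baseline to week 16. A shifted baseline reading therefore enters the outcome directly. Grip strength and gait speed are secondary endpoints and also feed the frailty classification, which is a main endpoint (section 7.3.4). Section 9 compares changes by unpaired t-test or Mann-Whitney test and specifies no adjustment for the baseline value. ANCOVA appears only in the list of abbreviations. Section 7.3.9 mentions the comorbidity index as a means of adjusting for confounding, but section 9 does not take that up.

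**Working it through.** **Inputs.** Block size 4 (sections 3 and 7.2), ratio 1:1 (section 7.2), 100 participants (section 4.5). The plan states no predictability figure to reproduce. Its sample size, used here only as the denominator, does reproduce: 42 per group with 15% dropout gives 42/0.85 = 49.4, rounded up to 50 per arm. 100 participants make 100/4 = 25 whole blocks.

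**Assumptions.** Allocations are released one at a time, and the recruiter knows all earlier ones in order. The documents do not say who is told of each allocation, or when.

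**Certain predictions.** The six equally likely blocks are AABB, ABAB, ABBA, BBAA, BABA and BAAB.
- The fourth place is always determined: 1 per block.
- The third place is determined when the first two match. This holds for AABB and BBAA, so the probability is 2/6 = 1/3.
- Expected number per block: 1 + 1/3 = 4/3. Share: (4/3)/4 = 33.3%. Over 25 blocks: 25 × 4/3 = 33.3 allocations.

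**Best guess (always name the arm that is behind).** The chance of being right by place is 1/2, 2/3, (1/3)(1) + (2/3)(1/2) = 2/3, and 1. The sum is 2.83, and 2.83/4 = 70.8%, against 50% with no information.

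**Sensitivity to how allocations are released and whether strata are used.**

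| Situation (blocks of 4) | Certain predictions |
|---|---|
| One at a time, no strata | 33.3% |
| 2, 4 or 8 equal strata (number assumed) | 32.5%, 31.6%, 30.0% |
| Released in batches of 2 | about 17% |
| Released in whole blocks of 4 | 0% |

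Stratifying would hardly change the figure. Batching would, but the documents describe none.

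**Alternatives.** For the random mixes, the recruiter is assumed to know the set of sizes but not their order (simulated over 100 allocations).

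| Scheme | Certain | Best guess right |
|---|---|---|
| Fixed 4 | 33.3% | 70.8% |
| Fixed 6 | 25% | 68.3% |
| Fixed 8 | 20% | 66.6% |
| Random 4 and 6 | 5.5% | 69.2% |
| Random 4, 6 and 8 | 2.3% | 67.9% |

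The random-mix rows do not force the list to end at exactly 100. If the total is fixed and known, the 100th allocation is always determined and those just before it sometimes are, so the certain share is a little above 2.3%. Varying the sizes removes most of the certainty. It does little for educated guessing.

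**The case against.** The strongest reply is that the arithmetic describes the worst case.

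- **Release and knowledge.** The 33.3% needs one-at-a-time release and full knowledge of earlier allocations. Any delay in learning them lowers it. This stands, so the figure is an upper bound. Section 7.4 places randomization within the baseline visit, which points to individual release, and no batching is described.
- **Section 5.** If its word variable is what was meant, the block is not fixed and the 33.3% does not apply. If its statement that investigators are blinded held, they would not know the earlier allocations. A reader might infer that the predictability holds whichever sentence is kept; the documents do not support that. Equally, section 5 does not rebut the point: it names only size four, and section 7.2 says blinding of the research team is not possible.
- **Existing safeguards.** A reader might infer that concealment here achieves nothing, or that selection bias will occur. Neither follows. Third-party custody, randomization after baseline, consecutive identification and mostly numeric criteria (age, gait speed, grip, MoCA-Ina, IADL) leave limited room for steering. What remains is timing, the judgement criteria and the team-measured baselines.
- **Analysis.** A reader might infer that no analysis could remove the resulting imbalance. True differences in measured baselines such as MoCA-Ina, grip and gait speed could be adjusted for. Unmeasured differences, and baseline readings that are themselves biased, could not be fully corrected that way. Section 9 plans no baseline adjustment in any case.

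**Conclusion.** The point holds as a quantified opportunity for selection bias. With the block size as printed in sections 3 and 7.2, up to 33.3% of allocations (about 33 of 100) can be inferred with certainty, and a best guess is right 70.8% of the time. This rests on sections 3 and 7.2 governing over section 5, on one-at-a-time release, and on a team that knows and tracks earlier allocations. The documents do not show that staff would act on it, and its effect on the results cannot be estimated from them. It is a cheap improvement worth making and does not invalidate the design. Sections 3, 5 and 7.2 need reconciling on block size in any event, and section 5 needs reconciling with sections 3 and 7.2 on blinding.

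**What to change.** - Have the same independent third party generate the list with randomly varying block sizes, for example 4, 6 and 8, constrained to total 100.
- Hold the sizes in a document that only that party can see.
- In sections 3, 5 and 7.2, replace the block-size wording with: *randomly varying block sizes, not disclosed to the research team*.
- If enrolment has begun, apply this to the remaining allocations.

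The constraint on the total matters. An unconstrained list cut at 100 could stop halfway through a block of 8 and leave the arms up to 4 apart (52 against 48). An intervention arm of 52 would exceed the 50 children paired 1:1 and the five groups of ten in section 5.1. Block sizes that sum to 100 keep the arms at 50 and 50.

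Release of each allocation after baseline is already planned and needs no change.

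**Cost.** A new computer-generated list and a wording amendment, with no extra staff. The last few allocations stay partly predictable because the total is fixed, and best-guess accuracy falls only from 70.8% to about 68%.
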